### **5.2.19        Electrotoretinography (ERG)**

Electrotoretinography testing of both eyes will be performed using the full field procedures conducted in accordance with standard protocol provided by the ERG Standardization Committee of the International Society for Clinical Electrophysiology of Vision (ISCEV) standards. Electrotoretinography will be performed at the [REDACTED] [REDACTED].

### **5.2.20        Visual Evoked Potentials (VEP)**

The pattern of visual evoked potentials will be obtained from each eye using a VEP stimulator according to standard protocols as described in the Study Procedures Manual.

### **5.2.21        Quality of Life Questionnaire (NEI VFQ-25)**

A member of the investigative team will administer the National Eye Institute (NEI) Visual Functioning Questionnaire (VFQ-25).

## **5.3 Treatment Administration**

RST-001 will be administered by intravitreal injection as specified in the Study Procedures Manual.

Prior to study treatment administration, the study eye of each patient will be prepared using the standard protocol as described in the Study Procedures Manual.

### **5.3.1 Post Injection Medications**

Topical corticosteroid treatment may be given to the injected eye according to the investigator's standard of care.

### **5.3.2 Management of Post Injection Intraocular Pressure**

The investigator shall have the ability to determine the optimum management of a raised intraocular pressure and may use any combination of topical IOP-lowering medications, oral acetazolamide or anterior chamber paracentesis in order to normalize the intraocular pressure.

## **6 Safety Assessments**

### **6.1 Overview of Safety Assessments**

Safety assessments in this study can be divided into measures of ocular safety and measures of systemic safety.

#### **6.1.1 Ocular Safety Measurements**

- Visual acuity as measured by low vision assessment of hand motion and light perception
- Evaluation of ocular inflammation. Parameters of anterior segment, vitreous and retinal/choroidal inflammation will be very carefully monitored
- Intraocular pressure measurement (IOP)
- Full dilated slit lamp biomicroscopy
- Color fundus photography and autofluorescence
- Electrotoretinography (ERG) to ISCEV standards
- Visual evoked potentials
- Full field sensitivity testing
- Spectral domain optical coherence tomography (SD-OCT) of the macula

### 6.1.1.1 Visual Acuity

- Visual acuity as measured by low vision of assessment of hand motion and light perception.

### 6.1.1.2 Ocular Inflammation

Owing to the potential for intraocular inflammation (as noted in the preclinical dog study) or immunogenicity, signs of ocular inflammation will be carefully monitored throughout the study and reported to the DSMC. Active inflammation of the anterior chamber, vitreous and retina/choroid will be documented in the case report forms according to recognized international criteria shown in [Table 4](#), below. Additional investigations, such as OCT and fluorescein angiography, may be performed at the discretion of the investigator according to clinical findings and accepted standards of care.

**Table 4 Biomicroscopic Grading of Anterior Chamber Cells and Flare**

This is compliant with the standardization of uveitis nomenclature [SUN] working group ([Jabs et al., 2005](#)).

#### (a) Anterior chamber cells

Grade	Cells/1mm 
0+	< 1 cell
0.5+	1-5
1+	6-15
2+	16-25
3+	26-50
4+	>50

#### Anterior chamber flare

Grade	Flare
0+	None
1+	Faint
2+	Moderate
3+	Marked
4+	Intense (including fibrin)

### Grading of Vitreous haze

Consistent with Nussenblatt RB, Palestine AG, Chan CC et al. Standardisation of vitreal inflammatory activity in intermediate and posterior uveitis ([Nussenblatt et al, 1985](#)).

Grade	Vitreous flare	Vitreous Haze	Clinical finding
0	None	No haze	Clear view of optic nerve
1	Minimal	Trace	Slight blurring of optic disc margin
2	Mild	1+	Slightly blurred optic nerve and vessels
3	Moderate	2+	Moderately blurred optic nerve and vessels
4	Marked	3+	Optic nerve head border blurry but visible
5	Severe	4+	Optic nerve head obscured

### 6.1.2 Systemic Safety Measurements

1. Patient-reported and investigator-reported adverse events (AEs)
2. Physical examination findings including vital signs
3. Findings of blood and serum laboratory testing
4. Findings of immunological testing
5. ECG and Chest X-ray results
6. Other clinical and laboratory testing performed by the investigator(s) based upon clinical observation, such as:
  - Vital signs
  - Clinical safety laboratory parameters
  - Immune response to RST-001 administration as measured by the testing detailed in Section [6.2.1](#) below.

[figure not shown]
### 6.2 Clinical Management of Safety Parameters

The need for additional clinical evaluations, assessments and visits shall be determined by the investigator(s) in accordance with accepted clinical practice and standards of care, where applicable. All activity will be recorded in the patient's source documentation.

Adverse events definitions and reporting requirements can be found in the Section [8.1](#) below.

### **6.2.1        Intraocular Inflammation and Immunogenicity Related to RST-001**

During the study, evidence of immune response to RST-001 will be monitored by systemic measurement of humoral and cellular immunity as follows:

These tests will be performed at several timepoints during the study:

There is no diagnostic test available for ocular immunogenicity. Instead, clinical evidence suggestive of immunogenicity will be gathered. Examination findings such as reduced visual acuity in the study eye, intraocular inflammation, uveitis, retinal vasculitis, retinal edema, hemorrhage, exudation and/or detachment will also be gathered. Additional evaluations such as OCT and fluorescein angiography may also aid the clinical identification of an immune response.

#### **Treatment of intraocular inflammation and immunogenicity**

In the event that immunogenicity is suspected by the investigator, topical, local, intraocular or systemic corticosteroid, corticosteroid-sparing and immunomodulatory therapy may be initiated, usually in an escalating fashion, in accordance with the investigator's practice, to control the inflammation. The patient will continue in the study and all additional assessments and visits will be documented in the source documents.

### **6.2.2        Complications of the Intravitreal Injection**

The complications of intravitreal injection commonly include mild conjunctival hyperemia and subconjunctival hemorrhage. Other uncommon complications include endophthalmitis, retinal tears/breaks/detachment, choroidal, vitreous and retinal hemorrhage.

In all instances, management of these complications will be determined by the investigator in accordance with his/her practice and standard-of-care, where applicable.

### **6.2.3        Occupational Safety**

The consequences of exposure of clinical personnel to the RST-001 drug are unknown. Precautions will be taken to avoid any exposure to the RST-001 product. No antidote is available for the RST-001 drug product.

## **6.2.4      Pregnancy and Exposure to RST-001 *In Utero***

Females who are pregnant at the Screening and/or Baseline visit will be excluded from the study. Females of child-bearing potential are required to maintain contraception during their participation in the study. In the event that a female becomes pregnant during the course of the study, the patient will continue to be followed in the study. The investigator should notify the sponsor within 24 hours of becoming aware that a female patient or female partner becomes pregnant during the course of the study. Female patients of childbearing potential will require a pregnancy test at Month 24 or early termination visit.

The potential effects of *in utero* exposure to RST-001 are not known.

## **7            Data Safety Monitoring Committee (DSMC)**

### **7.1            Composition**

An independent Data Safety Monitoring Committee (DSMC) will be formed to monitor the data from the study. The members of the DSMC will comprise ophthalmologists, physicians and statistician(s) with experience in this field of research.

### **7.2            Role**

The primary role of the DSMC is to ensure the protection and safety of patients participating in the study. The DSMC will review the general progress and conduct of the study and assist in resolving any issues that may arise. The composition and responsibilities, together with the agreed schedule for reviewing data will be detailed in the DSMC Charter.

### **7.3            Responsibilities**

1. Monitor and review safety and AE data of patients participating in the study.
2. Advise on dose-escalation, Phase 2a sample size/study population, study suspension or termination, as appropriate.
3. Provide review and advice on protocol amendments and changes to the clinical protocol, as appropriate.
4. Provide advice on any other matters as deemed necessary for the safe conduct of the study.
5. Provide assessment as to whether treatment benefits have been observed in Phase 1 of the study.

## 7.4 Enrollment Stopping Rules

Enrollment will be suspended pending a complete safety review by the sponsor of all patients including causality to determine the appropriateness of continuing dosing in the occurrence of the following events:

1. Any Grade 3 or greater AE related to RST-001 (according to Common Terminology Criteria for Adverse Events v4.03)
2. Occurrence of an intraocular infection related to contaminated RST-001 that required treatment would serve as a stopping rule
3. A safety issue has been identified that compromises the benefit or increases the risk balance

Dose-limiting toxicity (DLT) is defined as any adverse event of Grade 3 or higher that is expected to be related to the study treatment.

Dose escalation will stop if a DLT is observed, including:

4. Severe or persistent ocular inflammation
5. Other significant ocular toxicity (e.g., retinal detachment, evidence of direct toxicity)

## 8 Adverse Events

Adverse events occurring during the study will be recorded on an adverse event CRF. If adverse events occur, the first concern will be the safety of the study participants.

### 8.1 Definitions

#### 8.1.1 Adverse Event

An adverse event is any untoward medical occurrence in a subject or clinical investigation patient administered a pharmaceutical product and that does not necessarily have a causal relationship with this treatment. An adverse event can therefore be any unfavorable and unintended sign (including an abnormal laboratory finding), symptom, or disease temporally associated with the use of a medicinal (investigational) product, whether or not related to the medicinal (investigational) product. In addition, during the screening period, adverse events will be assessed regardless of the administration of a pharmaceutical product.

Note: Adverse events must be collected once informed consent has been obtained, regardless of whether or not the patient has been administered study treatment.

Progression of treatment indication including new or worsening of anticipated clinical signs or symptoms, which are collected as clinical efficacy variables and assessed as unequivocally associated with the disease progression and/or lack of efficacy, should NOT be reported as adverse events unless the disease progression is greater than anticipated in the natural course of the disease.

Adverse events will be assessed, documented, and recorded in the CRF throughout the study (ie, after informed consent has been obtained). At each visit, the investigator will begin by querying for adverse events by asking each patient a general, non-directed question such as “How have you been feeling since the last visit?” Directed questioning and examination will then be done as appropriate. All reported adverse events will be documented on the appropriate CRF.

### **8.1.2        Serious Adverse Event**

A serious adverse event is any adverse event occurring at any dose that results in any of the following outcomes: death, congenital anomaly or birth defect, significant disability, hospitalization, or life threatening. Important medical events that may not result in death, be life-threatening, or require hospitalization may be considered a serious adverse event when, based upon appropriate medical judgment, they may jeopardize the patient or patient and may require medical or surgical intervention to prevent one of the outcomes listed in this definition.

Allergan considers all cancer adverse events as serious adverse events. In addition, Allergan considers any abortion (spontaneous or nonspontaneous) as a serious adverse event.

Preplanned surgeries or procedures for pre-existing, known medical conditions for which a patient requires hospitalization is not reportable as a serious adverse event.

Any preplanned surgery or procedure should be clearly documented in the site source documents by the medically qualified investigator at the time of the patient’s entry into the study. If it has not been documented at the time of the patient’s entry into the study, then it should be documented as a serious adverse event and reported to Allergan.

### **8.1.3 Severity**

A clinical determination will be made of the intensity of an adverse event. The severity assessment for a clinical adverse event must be completed using the following definitions as guidelines:

Mild	Awareness of sign or symptom, but easily tolerated.
Moderate	Discomfort enough to cause interference with usual activity.
Severe	Incapacitating with inability to work or do usual activity.

### **8.1.4 Relationship to Study Drug or Study Procedure**

A determination will be made of the relationship (if any) between an adverse event and the study drug or study procedure, as applicable. A causal relationship is present if a determination is made that there is a reasonable possibility that the adverse event may have been caused by the drug or study procedure.

A study procedure occurring during the screening/baseline period can include a study required diagnostic procedure.

For treatment-related adverse events, the investigator will note on the CRF whether the event is related to the study drug, and/or the injection procedure.

## **8.2 Procedures for Reporting Adverse Events**

Any adverse event must be recorded on the appropriate CRF.

SARS-CoV-2 infections are to be captured as AEs. If the event meets the criteria for a serious adverse event, then follow the serious adverse event reporting directions.

Reactions known to be associated with the SARS-CoV-2 vaccine are to be reported as AEs. If the event meets the criteria for a serious adverse event, then follow the serious adverse event reporting directions.

All adverse events that are drug-related and unexpected (not listed as treatment-related in the current Investigator's Brochure) must be reported to the governing IRB as required by the IRB, local regulations, and the governing health authorities. Any adverse event that is marked "ongoing" at the exit visit must be followed-up as appropriate.

### 8.3 Procedures for Reporting a Serious Adverse Event

Any serious adverse event occurring during the study period (beginning with informed consent) and for at least 28 days after study exit must be immediately reported but no later than 24 hours after learning of a serious adverse event. Serious adverse events must be reported to Allergan (or Agent of Allergan) as listed on the Allergan Study Contacts Sheet and recorded on the serious adverse event form. All patients with a serious adverse event must be followed up and the outcomes reported. The investigator must supply Allergan and the IRB with any additional requested information (eg, autopsy reports and discharge summaries).

In the event of a serious adverse event, the investigator must:

1. Notify Allergan immediately by fax or email using the serious adverse event form (contact details can be found on page 1 of the serious adverse event form); phone numbers and relevant Allergan personnel contacts are also on the front page of protocol.
2. Obtain and maintain in his/her files all pertinent medical records, information, and medical judgments from colleagues who assisted in the treatment and follow-up of the patient.
3. Provide Allergan with a complete, written description of the adverse event(s) on the serious adverse event form describing the event chronologically, including any treatment given (eg, medications administered, procedures performed) for the adverse event(s). Summarize relevant clinical information about the event: signs, symptoms, diagnosis, clinical course and relevant clinical laboratory tests, etc. Include any additional or alternative explanation(s) for the causality which includes a statement as to whether the event was or was not related to the use of the investigational drug.
4. Promptly inform the governing IRB of the serious adverse event as required by the IRB, local regulations, and the governing health authorities.

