### **4.3 Method of Assigning Patients to Dose Groups**

This is a sequential dose-escalation study. In Phase 1, three groups comprising of approximately but no less than three patients, will be enrolled one after the other, receiving first the low dose, then the mid, and finally the high dose.

Escalation is dependent upon the enrollment stopping rules and DSMC recommendation.

In Phase 2a, up to approximately 12 patients may then be enrolled in parallel at the maximum tolerated dose.

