## **10 Clinical Monitoring Structure**

### **10.1 Monitoring**

A representative of the sponsor will monitor the study on a periodic basis. The determination of the extent and nature of monitoring will be based on considerations such as the objective, purpose, design, complexity, blinding, size, and endpoints of the study. Authorized representatives of Allergan or regulatory authority representatives will conduct on-site visits to review, audit and copy study-related documents. These representatives will meet with the investigator(s) and appropriate staff at mutually convenient times to discuss study-related data and questions. During the COVID-19 pandemic, remote data review/verification may be employed if allowed by the local regulatory authority, IRB/IEC, and the study site.

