## 20 Appendices

### 20.1 Appendix 1: Abbreviations

AAV	Adeno-associated Virus
AE	Adverse Event
ALT	Alanine Aminotransferase
AST	Aspartate aminotransferase
BCVA	Best Corrected Visual Acuity
°C	Degrees Celsius
CFR	Code of Federal Regulations
ChR2	Channelrhodopsin-2
COVID-19	Coronavirus disease - 2019
CRF	Case Report Form
CTC	Common Terminology Criteria for Adverse Events
DLT	Dose Limiting Toxicity
DNA	Deoxyribonucleic Acid
DSMC	Data Safety Monitoring Committee
ECG	Electrocardiogram
eCRF	Electronic Case Report Form
ERG	Electroretinography
ETDRS	Early Treatment for Diabetic Retinopathy Study
EVA	Electronic Visual Acuity
FDA	Food and Drug Administration, USA
FIH	First-in-Human
FFST	Full Field Sensitivity Testing
GCP	Good Clinical Practice
GLP	Good Laboratory Practice
GMP	Good Manufacturing Practice
IEC	Independent Ethics Committee
IND	Investigational New Drug
IOP	Intraocular Pressure
IRAE	Immediately Reportable Adverse Event
IRB	Institutional Review Board
ISCEV	International Society for Clinical Electrophysiology of Vision
mm	Millimeters
NEI	National Eye Institute
NIH	National Institutes of Health
OCT	Optical Coherence Tomography
QoL	Quality of Life
rAAV	Recombinant Adeno-associated Virus
RGC	Retinal Ganglion Cells
RP	Retinitis Pigmentosa
RST-001	RetroSense Therapeutics drug product (AGN-151597)
SARS-CoV-2	Severe Acute Respiratory Syndrome Coronavirus 2
SD-OCT	Spectral Domain - Optical Coherence Tomography
US	United States
VA	Visual Acuity
VEP	Visually Evoked Potential
VFQ	Visual Functioning Questionnaire

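### Related Grade 3+ events trigger the suspension and DLT rules whether or not they are serious, but only serious events must reach the sponsor within 24 hours

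*Protocol*

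**What the plan says.** **Triggers.** Protocol 7.4 suspends enrollment, pending a safety review by the sponsor, on "Any Grade 3 or greater AE related to RST-001" (graded by CTCAE v4.03) and on two other grounds. It stops dose escalation on a DLT, defined as "any adverse event of Grade 3 or higher that is expected to be related to the study treatment", and names severe or persistent ocular inflammation and significant ocular toxicity as included.

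**Reporting clock.** Under 8.3 a serious adverse event "must be immediately reported but no later than 24 hours after learning of a serious adverse event". Pregnancy, which the protocol does not count as an AE, also has a 24-hour limit. Section 8.1.2 defines seriousness by outcome. It adds a clause under which other important medical events may be classed as serious on medical judgment.

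**Other AEs.** Section 8.2 says: "Any adverse event must be recorded on the appropriate CRF". It also sends drug-related, unexpected AEs to the IRB, on whatever terms the IRB, local rules and health authorities set. Section 6.1.1.2 has signs of ocular inflammation reported to the DSMC. The protocol itself gives no time limit for any of these routes, and none requires notice to the sponsor.

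**Dosing pattern.** Section 3.15.1.1 puts at least one month and a DSMC review after the first patient in a group, then releases the rest of that group. Further DSMC reviews precede each escalation and Phase 2a. In Phase 2a, "up to approximately 12 patients may then be enrolled in parallel at the maximum tolerated dose" (4.3). Section 17 says that the study is multicenter.

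**The concern.** A suspension rule protects the next patient only if those who control the next injection learn of the event first. Here the rule runs on grade and relatedness, while the duty to tell the sponsor quickly runs on seriousness. An event can meet the first test and not the second. Severe intraocular inflammation managed without hospitalization is a plausible case, since the dog study (3.6.2.1) found dose-related ocular inflammation.

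For such an event, the party that 7.4 asks to carry out the safety review has no stated entitlement to prompt notice. Monitoring will not reliably supply it: "A representative of the sponsor will monitor the study on a periodic basis" (10.1), with no interval given. In a first-in-human study at several centers, with a product that cannot be removed from the eye once injected (3.13), another site could dose a patient after the rule has been met. The protocol does set fast routes to the sponsor elsewhere, for pregnancy (8.3) and for dosing deviations (4.10), so the omission stands out.

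**Working it through.** The plan gives no figure on this point, and its sample size was chosen empirically (11.3.1). The check has three parts: compare the texts, count who could be affected, and illustrate how often the route would be needed.

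**1. The route of a related, non-serious Grade 3+ event**

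- Does it meet the 7.4 suspension rule? Yes. Seriousness is not a condition.
- Is it a DLT? Yes, if relatedness is expected. Seriousness is not a condition here either.
- Does the 24-hour clock in 8.3 apply? No, unless the investigator uses the important-medical-event clause in 8.1.2.
- What else applies? CRF entry (8.2), the IRB if unexpected (8.2), and the DSMC if it is ocular inflammation (6.1.1.2). No deadline is stated in the protocol, and no notice to the sponsor is required.
- When inflammation is treated, 6.2.1 keeps the patient in the study and has the extra assessments and visits entered in source documents. It does not mention alerting the sponsor.
- Can a met rule be recognized from the CRF? Not reliably. Section 7.4 uses CTCAE grades, while 8.1.3 asks only for mild, moderate or severe.

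**2. Patients who could be injected after an unreported event**

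Inputs: three Phase 1 groups of 3, and 6 to 12 patients in Phase 2a (Table 1). The totals are 3×3 + 12 = 21, the stated maximum, and 3×3 + 6 = 15 with the smaller Phase 2a.

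An ungated batch is a set of patients with no stated review between them. Each Phase 1 group has one, made up of the 2 patients left after the first; the whole of Phase 2a is another. The first patient injected in a batch cannot be exposed by an event within that batch. A batch of size n therefore has at most n − 1 affected patients.

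- Phase 1: 3 × (2 − 1) = 3
- Phase 2a with 12 patients: 12 − 1 = 11, giving 3 + 11 = 14 of 21 (67%)
- Phase 2a with 6 patients: 6 − 1 = 5, giving 3 + 5 = 8 of 15 (53%)

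These are ceilings. They do not include late events. Each gate requires a minimum of one month, but inflammation in the dogs was observed from at least 5 weeks after injection. An event in a group that has passed its gate would then rely on the reporting route alone. The documents give no accrual rate, so no number is put on this.

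**3. How often the route would be needed (assumed rates)**

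The documents give no rate p of related, non-serious Grade 3+ events. The chance of at least one among n patients is 1 − (1 − p)^n:

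| Assumed p | n = 2 (rest of one Phase 1 group) | n = 12 (Phase 2a) |
|---|---|---|
| 5% | 10% | 46% |
| 10% | 19% | 72% |
| 20% | 36% | 93% |

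For example, at p = 10% and n = 12: 1 − 0.9^12 = 0.718.

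**The case against.** The strongest reply is that the protocol is less bare than the 24-hour rule suggests. Several parts of that reply stand.

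- **The event is not unknown.** A reader might infer that nobody would know the rule had been met. The documents do not support that: the treating investigator sees the event, 7.4 suspends enrollment when the event occurs rather than when a report arrives, and Section 12 makes the investigator responsible for patients' safety. What remains is that the sponsor and the other sites need not be told promptly.
- **CRF entry is not the only instruction.** The IRB and DSMC routes exist, and the DSMC route covers the most foreseeable event. They narrow the gap but carry no stated deadline and do not name the sponsor.
- **Many such events would be serious.** Section 8.1.2 includes significant disability and events that may need intervention to prevent a listed outcome. Retinal detachment, named in 7.4, could well be reported as an SAE. Because the clause is discretionary, some events remain outside it, in a number that cannot be estimated from the documents.
- **The share exposed is smaller than a simple count.** Adding up everyone in an ungated batch gives 3×2 + 12 = 18 of 21 (86%). That counts patients dosed without a review between them, including the first of each batch, so it overstates who could be injected after an unreported event.
- **The abbreviation list proves nothing.** It still carries "Immediately Reportable Adverse Event", which the current body text does not use. This is an editorial leftover, not evidence that a safety process was dropped.
- **Some material is unseen.** The DSMC Charter, to which 7.2 defers the review schedule, the Study Procedures Manual and Figure 1 were not available, and the synopsis describes enrollment as sequential. Any of these might add spacing or a faster route. The protocol text does not point to one for this purpose.

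**Conclusion.** The mismatch holds on the text. A related Grade 3+ event that is not serious can meet the suspension rule or be a DLT without any stated duty to tell the sponsor promptly. Further patients can then be injected before the sponsor or other sites are required to know.

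The within-batch ceiling is 14 of 21 patients, or 8 of 15 with the smaller Phase 2a, plus anyone dosed after a late event in a group already cleared. It is a count of patients who could be affected, not a forecast of harm.

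The conclusion rests on these assumptions:

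- Phase 1 groups have three patients. The protocol allows more, and each extra patient raises the ceiling by one.
- Phase 2a, which is optional, goes ahead.
- The documents not supplied contain no faster route.
- Patients remain to be dosed. The documents do not state enrollment status; if dosing is complete, the change protects no further patient in this study.

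The DSMC gates do catch events that appear before each review.

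**What to change.** Add one paragraph to 8.3 and cross-reference it in 7.4:

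- Any AE, serious or not, that may meet a 7.4 stopping criterion or the DLT definition is notified to the sponsor on the existing SAE form within the same 24 hours.
- The sponsor informs the DSMC and all dosing sites before the next scheduled injection.

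Also record the CTCAE grade on the AE CRF, beside the severity rating in 8.1.3, so that a met rule can be recognized. The same field would supply the Grade 3 criterion by which the synopsis and SAP 5.0 judge the therapy safe.

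This changes no dose, threshold or clinical rule. The cost is the protocol paragraph, site training, one CRF field and a few extra expedited reports in a study of about 21 patients.
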